## 17.2. Additional Information (for Japanese Study Sites Only)

## 17.2.1. GCP compliance

With regard to related regulations in Section 15.1 (for Japanese study sites only): This study will be conducted in compliance with the standards stipulated in Article 14-3 and Article 80-2 of the Pharmaceutical Affairs Law and by the "Ordinance Regarding Good Clinical Practice" (MHLW Ordinance No. 28, dated 27 Mar 1997) (referred to below as the "GCP Ordinance"). In compliance with the ethical principles of the Declaration of Helsinki, the human rights, welfare, and safety of the subjects will be the first considerations in the conducting of this study.

#### 17.2.2. Study Period

During 01 Nov 2016 to 31 Dec 2023.

# 17.2.3. Payment for Participation, Compensation for Study-Related Injuries, and Insurance

#### 17.2.3.1. Payment for Participation

If the subjects receive payment, the money will be paid to the subjects by the study site(s). That money will be taken from the fees paid by the Sponsor to each study site and will be paid in accordance with each study site's regulations.

#### 17.2.3.2. Compensation and Insurance

The Sponsor provides insurance for study subjects to make available compensation in case of study-related injury. Reimbursement, indemnity and insurance shall be addressed in Supplement 5.

## 17.3. Eastern Cooperative Oncology Group Performance Status Scale

GRADE	DESCRIPTION
0	Fully active, able to carry on all pre-disease performance without restriction
1	Restricted in physically strenuous activity, but ambulatory and able to carry out work of a light or sedentary nature, eg, light house work, office work
2	Ambulatory and capable of all self-care, but unable to carry out any work activities, up and about more than 50% of waking hours
3	Capable of only limited self-care, confined to bed or chair more than 50% of waking hours
4	Completely disabled. Cannot carry on any self-care. Totally confined to bed or chair
5	Dead

Source: Oken MM, Creech RH, Tormey DC, et al. Toxicity and response criteria of the Eastern Cooperative Oncology Group. Am J Clin Oncol. 1982;5(6):649-55.

## 17.4. Response Evaluation Criteria in Solid Tumors, Version 1.1

Tumor response will be assessed in accordance with the RECIST v1.1, described below. The details will be described in the Independent Review Charter developed by the imaging CRO selected by the Sponsor.

#### 17.4.1. Measurability of Tumor at Baseline

#### **17.4.1.1. Definitions**

At baseline, tumor lesions/lymph nodes will be categorized measurable or non-measurable as follows:

#### 17.4.1.1.1. Measurable

- Tumor lesions: Must be accurately measured in at least 1 dimension (longest diameter in the plane of measurement is to be recorded) with a minimum size of:
  - 10 mm by CT scan (CT scan slice thickness no greater than 5 mm)
  - 10 mm caliper measurement by clinical exam (lesions which cannot be accurately measured with calipers should be recorded as non-measurable)
  - 20 mm by chest X-ray
- Measurable malignant lymph nodes: To be considered pathologically enlarged and measurable, a lymph node must be ≥15 mm in short axis when assessed by CT scan (CT scan slice thickness recommended to be no greater than 5 mm). At baseline and in F/U, only the short axis will be measured and followed. See also notes below on "Baseline documentation of target and non-target lesions" for information on lymph node measurement.

#### **17.4.1.1.2.** Non-measurable

All other lesions, including small lesions (longest diameter <10 mm or pathological lymph nodes with  $\ge$ 10 to <15 mm short axis), as well as truly non-measurable lesions. Lesions considered truly non-measurable include: leptomeningeal disease, ascites, pleural or pericardial effusion, inflammatory breast disease, lymphangitic involvement of skin or lung, and abdominal masses/abdominal organomegaly identified by physical exam that is not measurable by reproducible imaging techniques.

#### 17.4.1.1.3. Special Considerations Regarding Lesion Measurability

Bone lesions, cystic lesions, and lesions previously treated with local therapy require particular comment.

#### 17.4.1.1.3.1. Bone Lesions

- Bone scan, positron emission tomography (PET) scan or plain films are not considered adequate imaging techniques to measure bone lesions. However, these techniques can be used to confirm the presence or disappearance of bone lesions.
- Lytic bone lesions or mixed lytic-blastic lesions, with identifiable soft tissue components, that can be evaluated by cross-sectional imaging techniques such as CT or MRI can be considered as measurable lesions if the soft tissue component meets the definition of measurability described above.
- Blastic bone lesions are non-measurable.

#### 17.4.1.1.3.2. Cystic Lesions

- Lesions that meet the criteria for radiographically defined simple cysts should not be considered as malignant lesions (neither measurable nor non-measurable) since they are, by definition, simple cysts.
- "Cystic lesions" thought to represent cystic metastases can be considered as measurable lesions, if they meet the definition of measurability described above. However, if noncystic lesions are present in the same subject, these are preferred for selection as target lesions.

#### 17.4.1.1.3.3. Lesions with Prior Local Treatment

• Tumor lesions situated in a previously irradiated area, or in an area subjected to other loco-regional therapy, are not considered measurable unless there has been demonstrated progression in the lesion.

#### 17.4.1.2. Specifications by Methods of Measurements

#### 17.4.1.2.1. Measurement of Lesions

All measurements should be recorded in metric notation, using calipers if clinically assessed. All baseline evaluations should be performed as close as possible to the treatment start and NEVER more than 28 days of the first dose of study drug administration.

#### 17.4.1.2.2. Method of Assessment

The same method of assessment and the same technique should be used to characterize each identified and reported lesion at baseline and during F/U. Imaging based evaluation should always be performed rather than clinical examination unless the lesion(s) being followed cannot be imaged but are assessable by clinical exam.

CT, MRI: CT is the best currently available and reproducible method to measure lesions selected for response assessment. This guideline has defined measurability of lesions on CT scan based on the assumption that CT slice thickness is 5 mm or less. When CT scans have slice thickness greater than 5 mm, the minimum size for a measurable lesion should be twice the slice thickness. MRI is also acceptable in certain situations (eg, for body scans).

## 17.4.2. Tumor Response Evaluation

#### 17.4.2.1. Assessment of Overall Tumor Burden and Measurable Disease

To assess objective response or future progression, it is necessary to estimate the overall tumor burden at baseline and use this as a comparator for subsequent measurements.

Only subjects with measurable disease at baseline should be included in the study.

#### 17.4.2.2. Baseline Documentation of "Target" and "Non-target" Lesions

When more than 1 measurable lesion is present at baseline, all lesions up to a maximum of 5 lesions total (representative of all involved organs) should be identified as target lesions and will be recorded and measured at baseline (this means in instances where subjects have only 1 or 2 organ sites involved a maximum of 2 and 4 lesions respectively will be recorded).

Target lesions should be selected on the basis of their size (lesions with the longest diameter), be representative of all involved organs, but in addition should be those that lend themselves to reproducible repeated measurements. It may be the case that, on occasion, the largest lesion does not lend itself to reproducible measurement in which circumstance the next largest lesion which can be measured reproducibly should be selected.

Lymph nodes merit special mention since they are normal anatomical structures which may be visible by imaging even if not involved by tumor. As noted above, pathological nodes which are defined as measurable and may be identified as target lesions must meet the criterion of a short axis of  $\geq 15$  mm by CT scan. Only the short axis of these nodes will contribute to the baseline sum. The short axis of the node is the diameter normally used by radiologists to judge if a node is involved by solid tumor. Nodal size is normally reported as 2 dimensions in the plane in which the image is obtained (for CT scan this is almost always the axial plane; for MRI the plane of acquisition may be axial, sagittal, or coronal). The smaller of these measures is the short axis. For example, an abdominal node which is reported as being 20 mm  $\times$  30 mm has a short axis of 20 mm and qualifies as a malignant, measurable node. In this example, 20 mm should be recorded as the node measurement. All other pathological nodes (those with short axis  $\geq$ 10 mm but  $\leq$ 15 mm) should be considered non-target lesions. Nodes that have a short axis  $\leq$ 10 mm are considered non-pathological and should not be recorded or followed.

A sum of the diameters (longest for non-nodal lesions, short axis for nodal lesions) for all target lesions will be calculated and reported as the baseline sum diameters. If lymph nodes are to be included in the sum, then as noted above, only the short axis is added into the sum. The baseline sum diameters will be used as reference to further characterize any objective tumor regression in the measurable dimension of the disease.

All other lesions (or sites of disease) including pathological lymph nodes should be identified as non-target lesions and should also be recorded at baseline. Measurements are not required and these lesions should be followed as "present," "absent," or in rare cases "unequivocal progression." In addition, it is possible to record multiple non-target lesions involving the same organ as a single item on the case record form (eg, "multiple enlarged pelvic lymph nodes" or "multiple liver metastases").

#### 17.4.2.3. Response Criteria

This section provides the definitions of the criteria used to determine objective tumor response for target lesions.

#### 17.4.2.3.1. Evaluation of Target Lesions

CR: Disappearance of all target lesions. Any pathological lymph nodes (whether target or non-target) must have reduction in short axis to <10 mm.

PR: At least a 30% decrease in the sum of diameters of target lesions, taking as reference the baseline sum diameters.

PD: At least a 20% increase in the sum of diameters of target lesions, taking as reference the smallest sum on study (this includes the baseline sum if that is the smallest on study). In addition to the relative increase of 20%, the sum must also demonstrate an absolute increase of at least 5 mm.

SD: Neither sufficient shrinkage to qualify for PR nor sufficient increase to qualify for PD, taking as reference the smallest sum diameters while on study.

#### 17.4.2.3.2. Special Notes on the Assessment of Target Lesions

**Lymph nodes:** Lymph nodes identified as target lesions should always have the actual short axis measurement recorded (measured in the same anatomical plane as the baseline examination), even if the nodes regress to below 10 mm on study. This means that when lymph nodes are included as target lesions, the "sum" of lesions may not be zero even if CR criteria are met, since a normal lymph node is defined as having a short axis of <10 mm. For PR, SD, and PD, the actual short axis measurement of the nodes is to be included in the sum of target lesions.

Target lesions that become "too small to measure": While on study, all lesions (nodal and non-nodal) recorded at baseline should have their actual measurements recorded at each subsequent evaluation, even when very small (eg, 2 mm). However, sometimes lesions or lymph nodes which are recorded as target lesions at baseline become so faint on CT scan that the radiologist may not feel comfortable assigning an exact measure and may report them as being "too small to measure." When this occurs, it is important that a value be recorded on the eCRF. If it is the opinion of the radiologist that the lesion has likely disappeared, the measurement

should be recorded as 0 mm. If the lesion is believed to be present and is faintly seen but too small to measure, a default value of 5 mm should be assigned (note: it is less likely that this rule will be used for lymph nodes since they usually have a definable size when normal and are frequently surrounded by fat such as in the retroperitoneum; however, if a lymph node is believed to be present and is faintly seen but too small to measure, a default value of 5 mm should be assigned in this circumstance as well). This default value is derived from the 5 mm CT slice thickness (but should not be changed with varying CT slice thickness). The measurement of these lesions is potentially non-reproducible, therefore providing this default value will prevent false responses or progressions based upon measurement error. To reiterate, however, if the radiologist is able to provide an actual measure, that should be recorded, even if it is below 5 mm.

Lesions that split or coalesce on treatment: When non-nodal lesions "fragment," the longest diameters of the fragmented portions should be added together to calculate the target lesion sum. Similarly, as lesions coalesce, a plane between them may be maintained that would aid in obtaining maximal diameter measurements of each individual lesion. If the lesions have truly coalesced such that they are no longer separable, the vector of the longest diameter in this instance should be the maximal longest diameter for the "coalesced lesion."

#### 17.4.2.3.3. Evaluation of Non-target Lesions

This section provides the definitions of the criteria used to determine the tumor response for the group of non-target lesions. While some non-target lesions may actually be measurable, they need not be measured and instead should be assessed only qualitatively at the time points specified in the protocol.

CR: Disappearance of all non-target lesions. All lymph nodes must be non-pathological in size (<10 mm short axis).

Non-CR/Non-PD: Persistence of 1 or more non-target lesion(s) and/or maintenance of tumor marker level above the normal limits.

PD: Unequivocal progression (see comments below) of existing non-target lesions.

#### 17.4.2.3.4. Special Notes on Assessment of Progression of Non-target Disease

The concept of progression of non-target disease requires additional explanation as follows:

When the subject also has measurable disease: In this setting, to achieve "unequivocal progression" on the basis of the non-target disease, there must be an overall level of substantial worsening in non-target disease such that, even in presence of SD or PR in target disease, the overall tumor burden has increased sufficiently to merit discontinuation of therapy. A modest "increase" in the size of 1 or more non-target lesions is usually not sufficient to quality for unequivocal progression status. The designation of overall progression solely on the basis of change in non-target disease in the face of SD or PR of target disease will therefore be extremely rare.

When the subject has only non-measurable disease: The same general concepts apply here as noted above, however, in this instance there is no measurable disease assessment to factor into the interpretation of an increase in non-measurable disease burden. Because worsening in

non-target disease cannot be easily quantified (by definition: if all lesions are truly non-measurable) a useful test that can be applied when assessing subjects for unequivocal progression is to consider if the increase in overall disease burden based on the change in non-measurable disease is comparable in magnitude to the increase that would be required to declare PD for measurable disease (ie, an increase in tumor burden representing an additional 73% increase in 'volume' [which is equivalent to a 20% increase diameter in a measurable lesion]). If 'unequivocal progression' is seen, the subject should be considered to have had overall PD at that point. While it would be ideal to have objective criteria to apply to non-measurable disease, the very nature of that disease makes it impossible to do so, therefore the increase must be substantial.

#### 17.4.2.3.5. New Lesions

The appearance of new malignant lesions denotes disease progression; therefore, some comments on detection of new lesions are important. There are no specific criteria for the identification of new radiographic lesions; however, the finding of a new lesion should be unequivocal: ie, not attributable to differences in scanning technique, change in imaging modality or findings thought to represent something other than tumor (for example, some "new" bone lesions may be simply healing or flare of preexisting lesions). This is particularly important when the subject's baseline lesions show PR or CR. For example, necrosis of a liver lesion may be reported on a CT scan report as a "new" cystic lesion, which it is not.

A lesion identified on a F/U study in an anatomical location that was not scanned at baseline is considered a new lesion and will indicate disease progression. An example of this is the subject who has visceral disease at baseline and while on study has a CT or MRI brain ordered which reveals metastases. The subject's brain metastases are considered to be evidence of PD even if he/she did not have brain imaging at baseline.

If a new lesion is equivocal, for example because of its small size, continued therapy and F/U evaluation will clarify if it represents truly new disease. If repeat scans confirm there is definitely a new lesion, then progression should be declared using the date of the initial scan.

#### 17.4.2.4. Evaluation of Best Overall Response

Best response in this study is defined as the best response across all time points (eg, a subject who has SD at first assessment, PR at second assessment, and PD on last assessment has a best overall response of SD). When SD is believed to be best response, it must also meet the protocol specified minimum time from baseline, 6 weeks ( $\pm$  7 days). If the minimum time is not met when SD is otherwise the best time point response, the subject's best response depends on the subsequent assessments. For example, a subject who has SD at first assessment, PD at second and does not meet minimum duration for SD, will have a best response of PD. The same subject lost to follow-up after the first SD assessment would be considered inevaluable.

The subject's best overall response assignment will depend on the findings of both target and non-target disease and will also take into consideration the appearance of new lesions.

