#### 2.1.1.3. Dose Expansion Part

The primary objective is as follows:

1. To assess safety and evaluate efficacy of U3-1402 at the RDEs in subjects with HER3-positive, HER2-negative (including HR-positive and TNBC) advanced/unresectable or metastatic breast cancers.

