### • Efficacy endpoints:

Tumor response will be evaluated using Response Evaluation Criteria in Solid Tumors (RECIST) version 1.1. Objective response rate (ORR) (the sum of complete response [CR] rate and partial response [PR] rate), disease control rate (DCR) (the sum of CR rate, PR rate, and stable disease [SD] rate), duration of response (DOR), clinical benefit rate (CBR; the proportion of subjects who achieved a best overall response of CR or PR or  $SD \ge 6$  months), time to response (TTR), PFS, OS, and percent change in target lesion(s).

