## 9. EFFICACY ASSESSMENTS

Efficacy endpoints will include ORR (the sum of CR rate and PR rate), DCR (the sum of CR rate, PR rate, and SD rate), DOR, CBR, TTR, PFS, OS, and percentage change in target lesion(s).

Tumor response will be evaluated using RECIST version 1.1 (Section 17.4) by the Investigator and the independent central imaging CRO selected by the Sponsor. Tumor assessments will be performed at screening and every 6 weeks in the first 24 weeks after Day 1 of Cycle 1 and every 12 weeks thereafter, independent of dosing schedule. Tumor assessments should not be delayed by dose interruptions; they are timed relative to Cycle 1, Day 1 and should continue until progressive disease or until a new anticancer therapy is started, whichever occurs first.

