## 11.6. Statistical Analysis Process

The clinical study will be analyzed by DS or its agent/CRO followed by this protocol, and SAP which will demonstrate all methodologies and displays/shells for statistical analyses.

The SAP will provide the statistical methods and definitions for the analysis of the efficacy and safety data, as well as describe the approaches to be taken for summarizing other clinical study information such as subject disposition, demographic and baseline characteristics, study drug exposure, and prior and concomitant medications. The SAP will also include a description of how missing, unused, and spurious data will be addressed.

To preserve the integrity of the statistical analysis and clinical study conclusions, the SAP will be finalized prior to database lock.

All statistical analyses will be performed using SAS® Version 9.3 or higher (SAS Institute, Cary, NC 27513).

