#### 17.4.2.4.3. Best Overall Response: All Time Points

The best overall response is determined once all the data for the subject is known.

Best response determination in this study where confirmation of CR or PR IS NOT required: Best response in this study is defined as the best response across all time points (eg, a subject who has SD at first assessment, PR at second assessment, and PD on last assessment has a best overall response of PR). When SD is believed to be best response, it must also meet the protocol specified minimum time from baseline, 6 weeks ( $\pm$  1 week). If the minimum time is not met when SD is otherwise the best time point response, the subject's best response depends on the subsequent assessments.

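### The best-overall-response example in Section 17.4.2.4 scores SD, PR, PD as SD, against its own rule and against the identical example in Section 17.4.2.4.3, which scores it as PR

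*Combined protocol and SAP*

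**What the plan says.** Section 17.4.2.4 takes the most favourable response over all assessments as the best response. Its example reads: "a subject who has SD at first assessment, PR at second assessment, and PD on last assessment has a best overall response of SD".

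Section 17.4.2.4.3 restates the rule under the lead-in "Best response determination in this study where confirmation of CR or PR IS NOT required". Its example is the same sequence with a different answer: "a subject who has SD at first assessment, PR at second assessment, and PD on last assessment has a best overall response of PR".

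Section 9 makes this text operative for both sets of readers: "Tumor response will be evaluated using RECIST version 1.1 (Section 17.4) by the Investigator and the independent central imaging CRO". Two further documents are to add to it. On response assessment, Section 17.4 says "The details will be described in the Independent Review Charter developed by the imaging CRO selected by the Sponsor"; on analysis, Section 11.6 says "The SAP will provide the statistical methods and definitions for the analysis of the efficacy and safety data".

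Section 2.3 defines the endpoint as "Objective response rate (ORR) (the sum of complete response [CR] rate and partial response [PR] rate". The primary objective of the Dose Expansion Part (Section 2.1.1.3) begins "To assess safety and evaluate efficacy of U3-1402 at the RDEs".

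**The concern.** Two assessors can each cite the protocol and classify the same subject differently, one as a responder and the other as a non-responder. The endpoints affected are these:

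- **ORR** changes directly, because only CR and PR count.
- **DOR and TTR** change through the set of responders they describe, on the usual reading that both are computed in responders.
- **CBR** can change, because SD counts only if it lasts at least 6 months, whereas PR counts regardless.
- **DCR** does not change, provided the SD meets the 6-week minimum, because SD and PR both count.

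ORR carries the efficacy part of the primary objective in the expansion cohorts, and Section 11.5 sizes those cohorts on it.

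**Working it through.** **1. Apply the rule to the sequence.** With the order CR > PR > SD > PD, the best of {SD, PR, PD} is PR. Section 17.4.2.4.3 reaches that answer; Section 17.4.2.4 does not.

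**2. Look for a provision that would make SD correct.** There are two candidates.
- *Minimum duration.* Both sections require SD to have lasted 6 weeks (± 7 days) from baseline. The requirement applies only when SD is the best response, so it cannot turn a PR into SD.
- *Confirmation.* If a PR had to be confirmed at a later scan, a single PR followed by PD would fall back to SD. Section 17.4.2.4.3 says confirmation is not required.

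Neither yields SD.

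**3. Reproduce the Section 11.5 figures.** Exact binomial, with X responders of n and one rule used throughout:

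| Cohort | Benchmark | P at null ORR (stated) | P at alternative ORR (stated) |
|---|---|---|---|
| HER3-high, HR-positive, n = 30 | X > 6 | 0.0258 at 0.10 (< 5%) | 0.8405 at 0.30 (> 80%) |
| HER3-low, HR-positive, n = 20 | X > 3 | 0.1330 at 0.10 (< 15%) | 0.7748 at 0.25 (> 75%) |
| HER3-high, TNBC, n = 30 | X > 9 | 0.0611 at 0.20 (< 10%) | 0.8237 at 0.40 (> 80%) |

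All stated bounds hold. The sample-size section is not in question.

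**4. Effect of one reclassified subject.** The shift in ORR is 1/n: 1/30 = 3.3 points, 1/20 = 5.0 points and 1/12 = 8.3 points. Cohort sizes come from Sections 3.1.4 and 11.5, taking the roughly 60 randomized subjects as 30 per dose. Section 11.4.1 plans exact 95% intervals. The Clopper-Pearson limits for x of n are the 0.025 quantile of Beta(x, n − x + 1) and the 0.975 quantile of Beta(x + 1, n − x). Starting from the lowest count above each benchmark:

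| Cohort | Scored PR | Scored SD |
|---|---|---|
| HER3-high, HR-positive | 7/30 = 23.3% (9.9–42.3) | 6/30 = 20.0% (7.7–38.6) |
| HER3-low, HR-positive | 4/20 = 20.0% (5.7–43.7) | 3/20 = 15.0% (3.2–37.9) |
| HER3-high, TNBC | 10/30 = 33.3% (17.3–52.8) | 9/30 = 30.0% (14.7–49.4) |

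**5. Effect if a share of responders is affected.** The documents give no such share, so f = 10%, 20% and 30% are assumptions. If a fraction f of responders had only a single PR and were scored SD, the response rate at the alternative becomes p1 × (1 − f); for the first cohort at f = 10%, 0.30 × 0.9 = 0.27. The probability of exceeding the benchmark is then:

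| Cohort | f = 0 | f = 10% | f = 20% | f = 30% |
|---|---|---|---|---|
| HER3-high, HR-positive | 0.840 | 0.738 | 0.604 | 0.447 |
| HER3-low, HR-positive | 0.775 | 0.690 | 0.589 | 0.474 |
| HER3-high, TNBC | 0.824 | 0.684 | 0.506 | 0.319 |

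**6. CBR.** Scans fall every 6 weeks for the first 24 weeks (Section 6.4.2). Suppose weeks 6, 12 and 18 give SD, PR and PD. Week 18 is day 126, and with the 7-day window PD falls on days 119 to 133. At 30.4375 days per month that is 3.9 to 4.4 months, short of 6 months (182.6 days). The subject counts toward CBR as PR but not as SD.

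**The case against.** The best counter-argument is that the protocol already settles the matter. The rule appears twice and gives PR both times; the SD answer is one word in a parenthetical example; and the later, dedicated subsection says in capitals that confirmation is not needed. A reader who applies the rule will not go wrong, and nothing shows that anyone has used the faulty example. The SAP and the Charter, not seen here, may also state the rule correctly. The benchmark counts above were chosen so that one subject crosses the line, and Section 11.5 attaches no decision to crossing it.

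Much of this stands. It looks like a drafting slip, the sizes are illustrative, and no result is shown to be wrong.

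A second objection concerns order. SD is what a confirmation rule would give, and Section 1.1 reports a confirmed ORR of 42.9% from this study, so the sponsor might first state which ORR is meant. That supports saying so explicitly. It does not support keeping SD, because the only sentence in the protocol that sets the rule says confirmation is not required. It also shows why the slip should not be left: someone who knows the confirmed figure could take the SD answer as intended.

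**Conclusion.** The concern holds. The Section 17.4.2.4 example contradicts the rule it illustrates and the matching example in Section 17.4.2.4.3, and nothing in the protocol makes SD the right answer. Followed literally, it removes a responder from ORR, at 3.3, 5.0 or 8.3 points per subject in cohorts of 30, 20 or 12.

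The total effect is unknown: it depends on how many subjects have this sequence and on whether any assessor or program follows the faulty example. The conclusion is limited to the protocol text and assumes that the no-confirmation statement expresses the study's intent. It should be fixed, but it does not undermine the design or the sample size.

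**What to change.** 1. In the Section 17.4.2.4 example, change the final answer from SD to PR, so that it matches Section 17.4.2.4.3.
2. Check that the SAP and the Independent Review Charter apply the same rule, for both Investigator and central assessments.
3. Optional, once step 2 is done: in Sections 11.4.1 and 11.5, label ORR as based on unconfirmed best overall response, so that it is not read alongside the confirmed ORR in Section 1.1 as the same quantity.

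The responder rule in Section 17.4.2.4.3 stays as it is.

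The cost is one word, a wording check of two documents and, if wanted, a phrase in two sections. Section 15.7 puts protocol changes through the usual amendment review, so the edit carries that overhead. No new scans or data are needed. No new analyses are needed either, provided existing outputs already follow Section 17.4.2.4.3; step 2 should establish that.
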